- **3.2.10** No concurrent anticoagulation with warfarin, heparin/heparin analogues, clopidogrel, direct thrombin inhibitors, or direct factor XA inhibitors.
- **3.2.11** No history of atrial fibrillation or myocardial infarction.
- **3.2.12** No history of grade 4 hypertension, defined as hypertension resulting in life-threatening consequences (e.g., malignant hypertension, transient or permanent neurologic deficit, hypertensive **crisis**).
- **3.2.13** No chronic (duration $>$ 30 days) daily use of oral steroids. Inhaled or topical steroids are allowed.
- **3.2.14** No known allergy to aspirin.
- **3.2.15** No prior invasive malignancy of any type within the past 5 years except for current diagnosis of breast cancer, and any prior diagnosis of basal or squamous cell carcinoma of the skin.

Prior history of in situ carcinoma is allowed.

Patients with a prior history of any type of breast cancer greater than 5 years from study screening may participate in this study.
- **3.2.16** Concurrent enrollment on a non-chemotherapy treatment trial will be allowed, as long as that trial allows concurrent daily aspirin use.
- **3.2.17** No history of metastatic breast cancer.

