8.2 Dose Modifications

8.2.1 Dose Levels

Dose Level	Drug Name	Dose
0*	Aspirin	300 mg
-1	Aspirin	100 mg

*Dose level 0 refers to the starting dose.

If dose reduction below level -1 is required, permanently discontinue protocol therapy.

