8.2.2 Hematologic Adverse Events

8.2.2.1 Grade 1 bleeding

For grade 1 bleeding, one level dose reduction will be allowed at physician discretion.

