8.2.2.4 Other grade 1 and 2 non-bleeding related gastrointestinal toxicity

A proton pump inhibitor will be prescribed for the patient at the discretion of the treating physician. Alternatively, at the discretion of the treating physician, one level dose reduction may be performed.

8.2.3 Cardiovascular toxicities and thrombotic events**8.2.3.1 For grade 3 or 4 cardiac ischemia/infarction or thrombosis: Permanently discontinue protocol therapy.****8.2.3.2 For grade 1 toxicity, no change in study drug dosage is required.**

For grade 2 toxicity, reduce to dose level -1, at physician discretion. If dose is reduced, patients should continue at this dose for the duration of study treatment.

8.2.4 Intracranial hemorrhage: Permanently discontinue protocol therapy for any grade intracranial bleeding.**8.2.5 Macular Degeneration: Permanently discontinue protocol therapy for any grade macular degeneration considered related to aspirin/placebo.****8.2.6 Tinnitus or hearing loss: Permanently discontinue protocol therapy for any grade considered related to aspirin/placebo.****8.2.7 Dermatologic toxicities: Permanently discontinue protocol therapy for Stevens-Johnson syndrome or toxic epidermal necrolysis.****8.2.8 Other non-hematologic toxicities attributed to aspirin/placebo**

For other grade 3 or 4 non-hematologic toxicities considered related to aspirin/placebo, interrupt aspirin/placebo, for a maximum of 28 days until toxicity improves to \leq grade 2, then resume aspirin/placebo, with one dose reduction.

For recurrence of the same grade 3 or 4 non-hematologic toxicity considered related to aspirin/placebo, or if toxicity does not improve after 28 days, permanently discontinue aspirin/placebo.

For persistent grade 2 non-hematologic toxicity considered related to aspirin/placebo that the patient finds unacceptable, interrupt aspirin/placebo for a maximum of 28 days until toxicity improves to \leq grade 1, then resume aspirin/placebo at the previous dose.

For recurrence of unacceptable grade 2 non-hematologic toxicity considered related to aspirin/placebo, or if grade 2 toxicity does not improve after 28 days, permanently discontinue aspirin/placebo.

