Methotrexate: Salicylate can inhibit renal clearance of methotrexate, leading to bone marrow toxicity, especially in the elderly or renally impaired.

Nonsteroidal Anti-Inflammatory Drugs (NSAIDs): Concomitant administration of NSAIDs and aspirin may lead to increased bleeding or decreased renal function. Avoid concurrent use.

Oral Hypoglycemics: Moderate aspirin doses may increase the effectiveness of oral hypoglycemic agents causing hypoglycemia.

Uricosuric Agents: (Probenecid and Sulfinpyrazone): Salicylates antagonize the uricosuric action of uricosuric agents.

Pharmacokinetics

Absorption: Immediate, rapid and completely absorbed from gastrointestinal tract.

Distribution: Widely distributed to all tissues and fluids in the body including the central nervous system (CNS) and breast milk and fetal tissues. The highest concentrations are found in the plasma, liver, renal cortex, heart and lungs. The protein binding of salicylate is concentration-dependent, i.e. non-linear.

Metabolism: Hydrolyzed to salicylate (active by esterases in GI mucosa, red blood cells, synovial fluid and blood; metabolism of salicylate occurs primarily by hepatic conjugation; metabolic pathways are saturable).

Excretion: Urine (75% as salicyluric acid, 10% as salicylic acid).

T1/2: Parent drug 15 to 20 minutes; Salicylates 3 hours.

Adverse Events

Cardiovascular: Cardiac arrhythmia, edema, hypotension, tachycardia.

Central Nervous System: Agitation, cerebral edema, coma, confusion, dizziness, fatigue, headache, hyperthermia, insomnia, lethargy, nervousness, Reye's syndrome.

Dermatologic: Skin rash, urticarial.

Endocrine & Metabolic: Acidosis, dehydration, hyperglycemia, hyperkalemia, hypernatremia (buffered forms), hypoglycemia (children).

Gastrointestinal: Gastrointestinal ulcer, duodenal ulcer, dyspepsia, epigastric distress, gastritis, gastrointestinal erosion, heartburn, nausea, stomach pain, vomiting.

Genitourinary: Postpartum hemorrhage, prolonged gestation, prolonged labor, proteinuria, stillborn infant.

Hematologic & Oncologic: Anemia, blood coagulation disorder, disseminated intravascular coagulation, hemolytic anemia, hemorrhage, iron deficiency anemia, prolonged prothrombin time, thrombocytopenia.

Hypersensitivity: Anaphylaxis, angioedema.

Neuromuscular & Skeletal: Acetabular bone destruction, rhabdomyolysis, weakness.

Otic: Hearing loss, tinnitus.

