Renal: Increased blood urea nitrogen, increased serum creatinine, interstitial nephritis, renal failure (including cases caused by rhabdomyolysis), renal insufficiency, renal papillary necrosis

Respiratory: Asthma, bronchospasm, dyspnea, hyperventilation, laryngeal edema, noncardiogenic pulmonary edema, respiratory alkalosis, tachypnea.

Miscellaneous: Low birth weight.

Postmarketing and/or case reports (Limited to important or life-threatening): Anorectal stenosis (suppository), atrial fibrillation (toxicity), cardiac conduction disturbance (toxicity), cerebral infarction (ischemic), cholestatic jaundice, colitis, colonic ulceration, coronary artery vasospasm, delirium, esophageal obstruction, esophagitis (with esophageal ulcer), macular degeneration (age-related), periorbital edema, rhinosinusitis.

- Nursing Guidelines
- 1. Patients may experience GI upset and or reflux. Treat symptomatically and monitor for effectiveness.
- 2. Aspirin can cause GI bleeding. Instruct patients to report any black tarry stools and/or hematemesis to the study team immediately.
- 3. Patients may experience increased bruising and/or bleeding. Instruct patients to report this to the study team.
- 4. Patients should be instructed not to take NSAID's in conjunction with aspirin. Concomitant use can lead to increased risk of bleeding and/or renal dysfunction.

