12.1.2 Early discontinuation of study agent

If protocol treatment is discontinued early for reasons other than patient death or the invasive disease events listed above, such as, adverse events from A011502 protocol therapy, physician discretion, patient withdrawal, early unblinding or extraordinary medical circumstances, continue to follow the patient according to [Section 12.2](#).

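### Section 8.2 has no stop rule for hypersensitivity, so a related grade 3-4 reaction on 300 mg defaults to resuming blinded drug at 100 mg

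*Combined protocol and SAP*

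**What the plan says.** Section 8.2.1 sets two dose levels: 300 mg (level 0, the starting dose) and 100 mg (level -1). A patient who would need to go lower comes off treatment: "If dose reduction below level -1 is required, permanently discontinue protocol therapy".

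Sections 8.2.2 to 8.2.7 give event-specific rules. Some are discretionary, for example "For grade 1 bleeding, one level dose reduction will be allowed at physician discretion". Others are absolute; the rule for tinnitus or hearing loss in 8.2.6 reads "Permanently discontinue protocol therapy for any grade considered related to aspirin/placebo".

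Section 8.2.8 covers every other related non-hematologic toxicity. At grade 3 or 4, study drug is interrupted for at most 28 days until the event is grade 2 or lower, and the site is to "then resume aspirin/placebo, with one dose reduction". Treatment ends permanently if the same grade 3-4 toxicity returns or if there is no improvement after 28 days.

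Section 10.1 lists among aspirin's adverse events "Hypersensitivity: Anaphylaxis, angioedema" and, under a separate organ class, "Respiratory: Asthma, bronchospasm, dyspnea, hyperventilation, laryngeal edema". The only allergy rule in the protocol is eligibility criterion 3.2.14: "No known allergy to aspirin".

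**The concern.** Severe allergic and airway reactions are foreseeable with aspirin, and the protocol itself lists them. A reader would expect them among the events that end treatment outright. Instead they are unnamed and drop into a general rule written for toxicities where a lower dose is a sensible response.

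A site that follows 8.2.8 literally would give blinded tablets, possibly 100 mg of aspirin, to a patient who has just had a grade 3 or 4 reaction attributed to those tablets. For a reaction that settles within the 28 days, the next mandatory stop is a second severe reaction. What is at stake is the safety of individual patients. The primary comparison, its power and its error rate are not affected.

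**Working it through.** No arithmetic beyond a ratio and a count is needed. The check is to trace one case through the rules and then see whether any other section intercepts it.

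**Step 1. Count the rules in 8.2 that stop treatment permanently at first occurrence.**

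| Section | Event | Threshold |
|---|---|---|
| 8.2.2.3 | GI bleeding | grade 3-4 |
| 8.2.3.1 | Cardiac ischemia/infarction or thrombosis | grade 3-4 |
| 8.2.4 | Intracranial bleeding | any grade |
| 8.2.5 | Macular degeneration | any grade, if related |
| 8.2.6 | Tinnitus or hearing loss | any grade, if related |
| 8.2.7 | Stevens-Johnson syndrome, toxic epidermal necrolysis | any occurrence |

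That makes six rules. Those naming anaphylaxis, angioedema, bronchospasm or laryngeal edema: 0 of 6. The nearest is 8.2.7, but it is headed as dermatologic and names only those two skin conditions.

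**Step 2. Trace the case.** A patient on level 0 has a related grade 3-4 reaction.

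- Nothing in 8.2.2 to 8.2.7 matches, so 8.2.8 governs.
- Study drug is interrupted. The 28 days are a maximum, and no minimum is stated. A reaction that settles quickly meets the condition for resuming.
- Study drug resumes at level -1. The re-exposure dose is 100/300 = 33% of the starting dose, still active drug in the aspirin arm.
- The formulation details in 10.1 give the 100 mg aspirin tablet the same active substance, fillers and coating ingredients as the 300 mg tablet. The two placebo strengths likewise share their ingredients. Lowering the dose therefore removes no component in either arm.

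A patient already on 100 mg is different. One further reduction would go below level -1, so 8.2.1 ends treatment. The gap is confined to patients on 300 mg, which is where everyone starts.

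**Step 3. Look for a rule elsewhere that intercepts the case.**

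- *3.2.14* applies at entry and to known allergy. A first reaction under blinding is only a suspected aspirin allergy and arises after entry.
- *12.1.2* includes among reasons for early discontinuation "such as, adverse events from A011502 protocol therapy, physician discretion, patient withdrawal, early unblinding or extraordinary medical circumstances". It tells sites to keep following such patients; it does not say when drug must stop.
- *8.3* requires discontinuation once a patient is unblinded, but unblinding needs authorisation by an executive officer. Its adverse-event example is an unexpected life-threatening event, whereas Section 9.3 treats events listed in Section 10.0 as expected.
- *9.3* requires expedited reports: for grade 4, within 24 hours with a full report 5 days later; for grade 3, within 10 calendar days. It contains no stop instruction. Because 8.2.8 sets no minimum interruption, a grade 3 report may arrive after drug has been resumed.

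None of these overrides 8.2.8.

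**Step 4. Compare within 8.2.** Discretion is written into 8.2.2.1, 8.2.2.4 and 8.2.3.2 but not into the grade 3-4 resume sentence of 8.2.8. Related tinnitus of any grade is a mandatory permanent stop, while related grade 4 anaphylaxis on 300 mg carries a default of resumption. The protocol gives no reason for the difference.

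**The case against.** The best reply is that nobody is forced to rechallenge. Section 12.1.2 recognises both adverse events and physician discretion as grounds for stopping, with no grade threshold, and Section 5.0 expects experienced physicians using their own judgment. A clinician who stops permanently after anaphylaxis is within the protocol. For harm to follow, someone would have to attribute a severe reaction to study drug and still restart it. Expedited reporting under 9.3 makes it more likely that such a restart would be noticed, and unblinding under 8.3 offers another route to a stop. On this view the defect is a missing sentence of minor weight.

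Much of that stands. Rechallenge is not compelled, and most clinicians would probably not do it. But the same could be said of Stevens-Johnson syndrome and intracranial bleeding, for which the sponsor still wrote mandatory stops. Having chosen explicit rules, the plan should not rely on sites setting aside its dose-modification text in order to be safe.

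Two further points are fair. Section 10.1 puts only anaphylaxis and angioedema under hypersensitivity; bronchospasm and laryngeal edema sit under respiratory events, so treating the four as one group is a clinical judgment that the documents do not settle. And no frequency can be shown. The first is a reason to leave the event list to safety physicians. The second means the weight of the point comes from the seriousness of a single event. Neither removes the gap.

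**Conclusion.** The concern holds. None of the six first-occurrence stop rules in 8.2 covers severe hypersensitivity, and the rule that does apply to a patient on 300 mg directs resumption at 100 mg. Followed as written, it re-exposes the patient to the suspected product, so this is more than an absent detail.

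The conclusion is limited to reactions that are grade 3 or 4, considered related to study drug, occurring on 300 mg, and improving to grade 2 or lower within 28 days. It rests on reading 8.2.8 as the residual rule for non-hematologic events not named elsewhere in 8.2. It asserts a written default, not that sites would follow it, and it claims no number of patients. It should be fixed because the possible harm is life-threatening and avoidable and the correction is small.

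**What to change.** Add a rule to 8.2 ending protocol therapy permanently for grade 3-4 hypersensitivity reactions (anaphylaxis, angioedema, bronchospasm, laryngeal edema) considered related to aspirin or placebo. State in 8.2.8 that these events are outside its resume rule. The sponsor's safety physicians should confirm the event list and the grade threshold.

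The cost is one new line and one exclusion, made by amendment. A few patients, some of them on placebo, may come off study drug sooner than they otherwise would. They remain in follow-up under 12.2 and are analysed in their assigned arm under 13.3.3, so the intention-to-treat comparison is untouched.

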8.2.9 Holding study drug for surgical procedures

Since aspirin can be associated with an increased risk of post-operative bleeding, some surgical procedures require stopping aspirin before and after a procedure. If the treating physician or surgeon determines that aspirin would be held for a procedure, then the study drug should be held for the same period of time. The total period that the study drug can be held for surgical procedures should not exceed 28 consecutive days.

8.3 Unblinding Procedures

Unblinding can be done only in cases of an emergency where knowledge of the treatment arm affects immediate medical management. Most medical emergencies and events attributed to study therapy can be adequately managed without knowledge of the treatment arm.

Follow the directions below for emergency unblinding procedures. Please note that if a treatment assignment is unblinded, the patient must discontinue protocol therapy, but will continue to be followed per [Section 12.2](#).

Emergency Unblinding Procedures:

Examples of emergencies include 1) a life-threatening unexpected adverse event that is at least possibly related to the investigational agent and for which unblinding would influence treatment decisions; or 2) medication error, such as accidental overdose. Expected adverse events are listed in the “Toxicities” section below.

Contact the Alliance Executive Officer on call by calling [REDACTED]
[REDACTED]

The institution must provide the following information to the Alliance Executive Officer:

- Alliance study ID (i.e., “A011502”)
- Alliance patient ID number (e.g., “999999”)
- Patient initials (e.g., “L,FM”)
- Institution name
- Name and telephone number of treating physician
- Name and contact information of person requesting the unblinding procedure
- Name and contact information of person to inform of treatment assignment
- Reason for emergency unblinding

Please remember that emergency unblinding request may be authorized only by an Alliance Executive Officer, and emergency unblinding applies only if unblinding would influence management of the medical situation.

After the Executive Officer deems unblinding is warranted, the treatment assignment will be provided to the contact person at the treating site.

9.0 ADVERSE EVENTS

The prompt reporting of adverse events is the responsibility of each investigator engaged in clinical research, as required by Federal Regulations. Adverse events must be described and graded using the terminology and grading categories defined in the NCI's Common Terminology Criteria for Adverse Events (CTCAE), Version 4.03. However, CTCAE v5.0 must be used for serious AE reporting through CTEP-AERS as of April 1, 2018. The CTCAE is available at ctep.cancer.gov/protocolDevelopment/electronic_applications/ctc.htm. Attribution to protocol treatment for each adverse event must be determined by the investigator and reported on the required forms. Please refer to the section on AE reporting procedures. NCI Guidelines: Adverse Event Reporting Requirements for further details.

9.1 Routine Adverse Event Reporting

Adverse event data collection and reporting, which are required as part of every clinical trial are done to ensure the safety of patients enrolled in the studies as well as those who will enroll in future studies using similar agents. Adverse events are reported in a routine manner at scheduled times according to the study calendar in Section 5.0. For this trial, the Adverse Events: Solicited form is used for routine AE reporting in Rave.

Solicited Adverse Events: The following adverse events are considered "expected" and their presence/absence should be solicited, and severity graded, at baseline and for each cycle of treatment.

• CTCAE v 4.03 Term	• CTCAE v4.0 Organ Class (SOC)
• Gastrointestinal bleeding	• Gastrointestinal disorders
• Intracranial hemorrhage	• Nervous system disorders
• Epistaxis	• Respiratory, thoracic and mediastinal disorders
• Hematuria	• Renal and urinary disorders
• Dyspepsia	• Gastrointestinal disorders
• Gastritis	• Gastrointestinal disorders
• Bruising	• Injury, poisoning and procedural complications

9.2 CTCAE Routine Reporting Requirements

In addition to the solicited adverse events listed in [Section 9.1](#), the following table outlines the combinations of time points, grades and attributions of AEs that require routine reporting to the Alliance Statistics and Data Center. Questions about routine reporting should be directed to the Data Manager.

***Combinations of CTCAE Grade & Attribution Required for Routine AE Data Submission on Case Report Forms (CRFs)**

Attribution	Grade 1	Grade 2	Grade 3	Grade 4	Grade 5
Unrelated			a	a	a
Unlikely			a	a	a
Possible		a	a, b	a, b	a, b
Probable		a	a, b	a, b	a, b
Definite		a	a, b	a, b	a, b

- a) Adverse Events: Other CRF - Applies to AEs occurring between registration and within 30 days of the patient's last treatment date, or as part of the Clinical Follow-Up Phase.
- b) Adverse Events: Late CRF - Applies to AEs occurring greater than 30 days after the patient's last treatment date.

9.3 Expedited Adverse Event Reporting (CTEP-AERS)

Investigators are required by Federal Regulations to report serious adverse events as defined in the table below. Alliance investigators are required to notify the Investigational Drug Branch (IDB), the Alliance Central Protocol Operations Program, the Study Chair, and their Institutional Review Board if a patient has a reportable serious adverse event. The descriptions and grading scales found in the NCI Common Terminology Criteria for Adverse Events (CTCAE) version 5 will be utilized for AE reporting beginning April 1, 2018. A copy of the CTCAE version 5.0 can be downloaded from the CTEP web site

All appropriate treatment areas should have access to a copy of the CTCAE. All reactions determined to be "reportable" in an expedited manner must be reported using the Cancer Therapy Evaluation Program Adverse Event Reporting System (CTEP-AERS).

For further information on the NCI requirements for SAE reporting, please refer to the 'NCI Guidelines for Investigators: Adverse Event Reporting Requirements' document published by the NCI.

Note: All deaths on study require both routine and expedited reporting regardless of causality. Attribution to treatment or other cause should be provided.

Death due to progressive disease should be reported as Grade 5 "Disease progression" in the system organ class (SOC) "General disorders and administration site conditions." Evidence that the death was a manifestation of underlying disease (e.g., radiological changes suggesting tumor growth or progression: clinical deterioration associated with a disease process) should be submitted.

9.3.1 Late Phase 2 and Phase 3 Studies: Expedited Reporting Requirements for Adverse Events that Occur on Studies under an IND/IDE \leq 30 Days of the Last Administration of the Investigational Agent/Intervention ^{1,2}

FDA REPORTING REQUIREMENTS FOR SERIOUS ADVERSE EVENTS (21 CFR Part 312)

NOTE: Investigators **MUST** immediately report to the sponsor (NCI) **ANY** Serious Adverse Events, whether or not they are considered related to the investigational agent(s)/intervention (21 CFR 312.64)

An adverse event is considered serious if it results in **ANY** of the following outcomes:

- 1) Death
- 2) A life-threatening adverse event
- 3) An adverse event that results in inpatient hospitalization or prolongation of existing hospitalization for \geq 24 hours
- 4) A persistent or significant incapacity or substantial disruption of the ability to conduct normal life functions
- 5) A congenital anomaly/birth defect.
- 6) Important Medical Events (IME) that may not result in death, be life threatening, or require hospitalization may be considered serious when, based upon medical judgment, they may jeopardize the patient or subject and may require medical or surgical intervention to prevent one of the outcomes listed in this definition. (FDA, 21 CFR 312.32; ICH E2A and ICH E6).

ALL SERIOUS adverse events that meet the above criteria **MUST** be immediately reported to the NCI via CTEP-AERS within the timeframes detailed in the table below.

Hospitalization	• Grade 1 Timeframes	• Grade 2 Timeframes	• Grade 3 Timeframes	Grade 4 & 5 Timeframes
Resulting in Hospitalization \geq 24 hrs		10 Calendar Days		24-Hour; 5 Calendar Days
Not resulting in Hospitalization \geq 24 hrs	Not required		10 Calendar Days	

NOTE: Protocol specific exceptions to expedited reporting of serious adverse events are found in the Specific Protocol Exceptions to Expedited Reporting (SPEER) portion of the CAEPR

Expedited AE reporting timelines are defined as:

- “24-Hour; 5 Calendar Days” - The AE must initially be reported via CTEP-AERS \leq 24 hours of learning of the AE, followed by a complete expedited report \leq 5 calendar days of the initial 24-hour report.
- “10 Calendar Days” - A complete expedited report on the AE must be submitted \leq 10 calendar days of learning of the AE.

¹ Serious adverse events that occur more than 30 days after the last administration of investigational agent/intervention and have an attribution of possible, probable, or definite require reporting as follows:

Expedited 24-hour notification followed by complete report \leq 5 calendar days for:

- All Grade 4, and Grade 5 AEs

Expedited 10 calendar day reports for:

- Grade 2 adverse events resulting in hospitalization or prolongation of hospitalization
- Grade 3 adverse events

² For studies using PET or SPECT IND agents, the AE reporting period is limited to 10 radioactive half lives, rounded UP to the nearest whole day, after the agent/intervention was last administered. Footnote “1” above applies after this reporting period.

NOTE: Deaths clearly due to progressive disease should be reported via CTEP AERS

- Expedited AE reporting timelines defined:
 - ➤ “24 hours; 5 calendar days” – The investigator must initially report the AE via CTEP-AERS \leq 24 hours of learning of the event followed by a complete CTEP-AERS report \leq 5 calendar days of the initial 24-hour report.
 - ➤ “10 calendar days” - A complete CTEP-AERS report on the AE must be submitted \leq 10 calendar days of the investigator learning of the event.
- Any medical event equivalent to CTCAE grade 3, 4, or 5 that precipitates hospitalization (or prolongation of existing hospitalization) must be reported regardless of attribution and designation as expected or unexpected with the exception of any events identified as protocol-specific expedited adverse event reporting exclusions (see below).
- Any event that results in persistent or significant disabilities/incapacities, congenital anomalies, or birth defects must be reported via CTEP-AERS if the event occurs following treatment with an agent under a CTEP IND.
- Use the NCI protocol number and the protocol-specific patient ID provided during trial registration on all reports.

Additional Instructions or Exclusion to CTEP-AERS Expedited Reporting Requirements for Phase 2 and 3 Trials Utilizing an Agent Under a CTEP IND or non-CTEP IND:

- All adverse events reported via CTEP-AERS (i.e., serious adverse events) should also be forwarded to your local IRB.
- Grade 3/4 hematosuppression and hospitalization resulting from such do not require CTEP-AERS, but should be submitted as part of study results. All other grade 3, 4, or 5 adverse events that precipitate hospitalization or prolong an existing hospitalization must be reported via CTEP-AERS.
- A secondary malignancy is a cancer caused by treatment for a previous malignancy (e.g., treatment with investigational agent/intervention, radiation or chemotherapy). A secondary malignancy is not considered a metastasis of the initial neoplasm.

CTEP requires all secondary malignancies that occur following treatment with an agent under an NCI IND/IDE be reported via CTEP-AERS. Three options are available to describe the event:

- Leukemia secondary to oncology chemotherapy (e.g., acute myelocytic leukemia [AML])
- Myelodysplastic syndrome (MDS)
- Treatment-related secondary malignancy

Any malignancy possibly related to cancer treatment (including AML/MDS) should also be reported via the routine reporting mechanisms as outlined in the protocol.

- A second malignancy is one unrelated to the treatment of a prior malignancy (and is NOT a metastasis from the initial malignancy). Second malignancies require ONLY routine reporting unless otherwise specified.
- All new malignancies must be reported via CTEP-AERS whether or not they are thought to be related to either previous or current treatment. All new malignancies should be reported, i.e. solid

tumors (including non-melanoma skin malignancies), hematologic malignancies, myelodysplastic syndrome/acute myelogenous leukemia, and in situ tumors. Whenever possible, the CTEP-AERS reports for new malignancies should include tumor pathology, history or prior tumors, prior treatment/current treatment including duration, any associated risk factors or evidence regarding how long the new malignancy may have been present, when and how the new malignancy was detected, molecular characterization or cytogenetics of the original tumor (if available) and of any new tumor, and new malignancy treatment and outcome, if available.

- Treatment expected adverse events include those listed in Section 10.0 and in the package insert.
- When submitting CTEP-AERS reports for “Pregnancy”, “Pregnancy loss”, or “Neonatal loss”, the Pregnancy Information Form should be completed and submitted, along with any additional medical information (form is available on the CTEP website at [REDACTED]). The potential risk of exposure of the fetus to the investigational agent(s) or chemotherapy agent(s) should be documented in the “Description of Event” section of the CTEP-AERS report.

In CTCAE v5.0, pregnancy loss is defined as “Death in utero,” and any pregnancy loss should be reported expeditiously as Grade 4 “Pregnancy loss” under the Pregnancy, puerperium and perinatal conditions SOC. A pregnancy loss should NOT be reported as a Grade 5 event under the Pregnancy, puerperium perinatal conditions SOC, as currently CTEP-AERS recognizes this event as a patient death.

A neonatal death should be reported expeditiously as Grade 4, “Death neonatal” under the General disorders and administration SOC.

